Sample Size and Power. Statistical power analyses examined the sample size requirements to detect greater than chance group differences on primary outcome (Primary Hypotheses 1 and 2). Because two primary hypotheses have been proposed, the Hochberg alpha adjustment will be used in hypothesis testing. The smaller of those sequential alpha-levels of $.025 (=0.05/2)$ was used in our estimates of the multiplicity-adjusted sample sizes. Preliminary data have traditionally been used for this purpose, but the small sample of the pilot data to provide estimates that are too imprecise for sample size calculations [70]. The power analyses examined the sample sizes required to detect clinically meaningful group differences in the VL suppression rate over time (i.e., the slope). Statistical power was estimated in a Monte-Carlo simulation study using SAS PROC MIXED over 1000 iterations. This represents the differential course for the two interventions over time. Based on the results, the protocol requires recruitment of 190 participants ($\approx 95/\text{group}$ at 1st stage) with $\approx 50\%$ non-responder in 2nd stage. The power table above shows the statistical power to detect standardized interaction effects of various magnitudes (0.45 to 0.55) for the Ns and a two-tailed alpha-level of 0.025. The intra-class correlation coefficient within subjects varied (ICC: .30, .40, .50, based on pilot data). The sample size of 95/group provides sufficient statistical power to detect differences in slopes that results in endpoint differences of $.45 \text{ sd. units}$ with $\text{ICC}=.30$ or .40 and 0.50. In the power analysis it is assumed about 50% responder state at the end of stage 1, thus resulting about 95 subjects in responder and non-responder group.

Strategies for Attrition. Attrition introduces bias and reduces power, precision and generalizability [71]. In keeping with the Intent-to-Treat principle we distinguish between intervention and study termination (complete withdrawal). Accordingly, we will make every effort to continue assessments for the entire course of randomized intervention,

PROTOCOL TITLE: ATN 144 SMART

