1.1 Data Management and Data Quality

The first randomization involves allocation to CPS vs. SMS using a 1:1 allocation ratio. This step will use stratified randomization in permuted blocks to achieve balance in distribution of behaviorally and perinatally infected youth. The REC data team will program the randomizer in Qualtrics and will not participate either in the intervention delivery or in the adherence reinforcement steps. The protocol team will monitor race, ethnicity, and gender to ensure balanced distribution at the first stage. After 6 months, stratified randomization will occur with permuted blocks within each trajectory. Since second stage randomization is dependent on first stage response status, we will only maintain the balance within each first stage treatment outcome when randomizing at the second stage.

Following the Analytic Core's (AC) standard quality assurance, including checking for outliers and abnormal values using graphical methods, we will verify that the distributions of measures meet the assumptions of the statistical tests to be used, applying a formal test such as the Shapiro-Wilk's test [60]. Transformations will be used when distributional assumptions are not fulfilled. Tests will be conducted to identify potential relationships among baseline demographic and clinical variables and our dependent variables and to see whether they are balanced between groups. If a baseline variable is not balanced between groups and is correlated with the dependent variable ($r > .30$), we will include this variable as a covariate in subsequent analyses. Since we will test more than one primary hypothesis with one primary outcome variable (VL suppression), the Hochberg step-up multiplicity adjustment will be used with a two-tailed family wise alpha-level of .05 [61]. All other tests described below will each have a two-tailed alpha-level of 0.05. Outcome analyses will be based on the principle of intention-to-treat [62].

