- 2) In case it fails to agree at least 80% cases, we will analyze VLS and SRA as two separate primary outcomes. Two measures cannot be combined, as they do not match sufficiently. In this situation, it is likely that VLS as primary outcome will not have sufficient sample size to produce an appropriately powered analysis, albeit, SRA may still produce a powered analysis provided SRA is available for all subjects. Note though no conclusion about VLS can be drawn from the outcome of SRA analysis.

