1.2.1 Primary Analysis Plan

The primary analysis will be a comparison of SRA (primary outcome) between the CPS and the SMS group at the end of first stage of randomization. This will be performed using a χ^2 test. We will also compare the VL suppression between the two groups for those available subjects, albeit this is no longer treated as primary outcome. Since SRA (and VL) is a continuous measure, we will use two-sample t-test to conduct this analysis. We will also compare the self-reported medication adherence rate (secondary outcome) between the two groups using a χ^2 test. All the primary analyses will be based on initial assignment to groups, using the ITT principle. Each of the primary hypotheses will be tested using linear mixed-effects (LME) regression analyses.¹⁰⁴ For testing primary hypothesis 1 (PH1), the model will include up to 3 repeated assessments of VL suppression (weeks 0/baseline, 12, 24, 36, 48). For primary hypothesis 2 (PH2), we will only focus on non-responders (for both CPS and SMS at stage 1) and compare the SRA as dependent variable using a repeated measure LME (weeks 0/baseline, 12, 24, 36, 48). In an effort to get the outcome for PH2 some subject may have final outcome at latter date than 48 weeks. Each LME model will include a random intercept and slope and fixed effects for adherence intervention group, and time, as well as the stratification variables: clinical site, age, gender. A likelihood ratio test will examine the incremental contribution of the group by time interaction, which represents the interaction of interest for PH1 and PH2, testing for a differential adherence intervention effect over time. The decision rule for each primary hypothesis calls for rejection of H_0 if this interaction is statistically significant using the Hochberg adjustment. A site by group interaction will be also examined and included in each model (above) if significant at the 0.05 level. The purpose of the LME based analysis for the primary aim is to determine which of the first-stage intervention, CPS or SMS, is associated with the most improvement in VL and adherence, regardless of which second-stage treatment participants received. Due to contraction of sample size compared to our original plan, we do not plan to adjust α for multiple of testing. In addition to PH1, for those subjects we have VL suppression data available we would perform similar LME to test for its significance. We also expect some subjects with complete VL data and many with partial VL data for

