1.2.4 Sample Size and Power

Sample Size and Power. Statistical power analyses examined the sample size requirements to detect greater than chance group differences on primary outcome (PH1 and Ph2). We have used Susan's formula with a total sample size of 120.

<http://people.seas.harvard.edu/~samurphy/papers/APPProof.pdf>

| Power Table | | | |
|--------------------|------------|------------|-----------------------------|
| ES | p | N | N(10% attrition adjustment) |
| 0.55 | 0.4 | 86 | 96 |
| | 0.5 | 104 | 116 |
| | 0.6 | 130 | 144 |
| | 0.7 | 174 | 192 |
| 0.6 | 0.4 | 74 | 80 |
| | 0.5 | 88 | 98 |
| | 0.6 | 110 | 120 |
| | 0.7 | 146 | 160 |

Alternatively, for the two groups comparison this corresponds to n=60/group. This sample size is sufficient to provide 80% power (or more) for a standardized Effect Size (ES) of 0.55 or more, using a t-distribution for a two tailed test with $\alpha=0.05$, with 10% attrition assuming equal responder rate (p) in both arms.

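### The SAP sets two incompatible alpha rules for the two primary hypotheses: Hochberg at family-wise 0.05, and no adjustment at all

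*SAP*

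**What the plan says.** Four places in the SAP bear on the alpha level for the primary tests.

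- **SAP 1.1, Data Management and Data Quality:** "the Hochberg step-up multiplicity adjustment will be used with a two-tailed family wise alpha-level of .05". The reason given is that there is more than one primary hypothesis. All other tests already run at 0.05 each.
- **SAP 1.2.1, decision rule:** for each of PH1 and PH2 the null is rejected "if this interaction is statistically significant using the Hochberg adjustment".
- **SAP 1.2.1, three sentences later:** "Due to contraction of sample size compared to our original plan, we do not plan to adjust" alpha for multiple testing.
- **SAP 1.2.4, Sample Size and Power:** 60 per group, 10% attrition and an effect size of 0.55 are said to give at least 80% power, "using a t-distribution for a two tailed test with $\alpha=0.05".

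Protocol 16.0 keeps Hochberg in its data-quality paragraph and in its decision rule. Its power paragraph, for 190 participants, takes the smaller Hochberg level of 0.025, which "was used in our estimates of the multiplicity-adjusted sample sizes".

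The set of primary outcomes is also unsettled. If viral load suppression (VLS) and self-reported adherence (SRA) agree in fewer than 80% of cases, SAP 1.2 says "we will analyze VLS and SRA as two separate primary outcomes" and gives no alpha rule for that case. SAP 1.2.1 says of VL suppression: "albeit this is no longer treated as primary outcome".

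**The concern.** Both rules are current text in the same paragraph, and they can give opposite verdicts on a primary hypothesis. Hochberg rejects both hypotheses if the larger p-value is at most 0.05; otherwise it rejects only the one with the smaller p-value, and only if that is at most 0.025. The unadjusted rule rejects any hypothesis with p at most 0.05. They part when one p-value is above 0.025 and at most 0.05 and the other is above 0.05. The first hypothesis is then rejected under one sentence and not under the other, so the choice could be made after the results are known.

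The no-adjustment sentence cannot be read as covering only secondary tests. SAP 1.1 already leaves those unadjusted, so the sentence has an effect only if it reaches PH1 and PH2. SAP 1.2 also carries a note that some original aims were not completed because of low retention, so the text was edited after retention was known. That does not show that anyone had seen outcomes by arm, but it makes a single clear rule more important.

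**Working it through.** **Inputs.** Two primary hypotheses, each with its own rejection rule (SAP 1.2.1). Family-wise 0.05, two-sided (SAP 1.1). 60 per group, 10% attrition, effect size (ES) 0.55, responder rate p from 0.4 to 0.7 (SAP 1.2.4). Evaluable per group: 60 × 0.9 = 54.

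**Assumptions.** PH1 and PH2 tests are independent. Power is for a two-sample t-test, as in the SAP's power statement; the decision test itself is a mixed-model group-by-time interaction, which was not modelled. For PH2, non-responders are taken as 54 × (1 − p) per arm.

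**1. Reproduce the SAP's own figure.** The table follows N = 2(z₁₋α/₂ + z₀.₈₀)² / [ES²(1 − p)]. At ES 0.55 and p = 0.5:

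- α = 0.05: N = 103.8, against 104 in the table; 104/0.9 = 115.6, so 116, as in the table.
- α = 0.025: N = 125.7, which does not match.

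All eight N values match α = 0.05 within small rounding; none matches 0.025.

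**2. Family-wise error, both nulls true.**

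- Unadjusted: 1 − 0.95² = 0.0975.
- Hochberg: 0.05² + 2 × 0.025 × 0.95 = 0.0500.
- The rules disagree with probability 2 × 0.025 × 0.95 = 0.0475, the difference between the two.
- If the two tests are correlated, the unadjusted error is 9.59% at 0.25, 9.07% at 0.5 and 8.10% at 0.75. Under any dependence it is at most 10%.

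**3. PH1 power, 54 per group, ES 0.55 (noncentral t).** 0.808 at α = 0.05 and 0.720 at α = 0.025. Under Hochberg, PH1 power = 0.720 + (0.808 − 0.720) × P(PH2 p ≤ 0.05). With PH2 null this is 0.720 + 0.088 × 0.05 = 0.724. With PH2 also at ES 0.55:

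| Responder rate | PH2 n per arm | PH2 power at 0.05 | PH1 power, Hochberg | P(rules disagree) |
|---|---|---|---|---|
| 0.7 | 16.2 | 0.329 | 0.749 | 0.078 |
| 0.6 | 21.6 | 0.423 | 0.757 | 0.072 |
| 0.5 | 27.0 | 0.509 | 0.765 | 0.066 |
| 0.4 | 32.4 | 0.587 | 0.772 | 0.059 |

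**4. Disagreement if PH1 has ES 0.55 and PH2 is null.** (0.808 − 0.720) × 0.95 + 0.025 × (1 − 0.808) = 0.089, using unrounded powers.

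**5. Size for 80% PH1 power at 0.025.** By noncentral t, 65 per group; 130/0.9 = 144.4, so 145 enrolled. By the normal approximation that reproduces the SAP table, 63 per group; 126/0.9 = 140 enrolled.

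**6. Fixed order, PH1 then PH2, each at 0.05.** PH1 power stays at 0.808. PH2 power at 50% responders is 0.808 × 0.509 = 0.412, against 0.487 under Hochberg.

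**7. Agreement below 80%.** If both outcomes were primary for both hypotheses, there would be four unadjusted tests: 1 − 0.95⁴ = 18.5% under independence, with a strict bound of 4 × 0.05 = 20%. The documents give no correlation between the VLS and SRA tests; assumed values of 0.3, 0.5, 0.7 and 0.9 give 18.1%, 17.3%, 16.0% and 13.6%.

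**The case against.** The best defence is that the intent can be read. SAP 1.1 repeats the protocol's paragraph and still names VL suppression as the one primary outcome, which SAP 1.2 replaces. The no-adjustment sentence is the only statement on multiplicity tied to the revised design, and SAP 1.2.4 works at 0.05. On that reading the Hochberg text is left over. PH1 and PH2 also concern different randomizations and populations, so testing each at 0.05 without family-wise control, and saying so, is an arguable choice.

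That intent is plausible, but it does not settle the matter. The Hochberg decision rule in SAP 1.2.1 was reworded from the protocol and kept, and SAP 1.1 still promises family-wise 0.05. The co-primary label in SAP 1.2 does not help, because success on both hypotheses is not required. Open disclosure would remove the contradiction, but would not deliver the stated 5%.

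Some limits on the numbers stand:

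- The PH2 figures, and the Hochberg power and disagreement figures that use them, are illustrative. Protocol 5.0 counts participants without a 3-month viral load as non-responders, and Protocol 13.0 gives no further randomization to those who refuse the intervention, so PH2's size need not follow the response rate.
- A power statement at 0.05 is not wholly foreign to Hochberg, which tests the larger p-value at 0.05. The fair criticism is that the SAP no longer uses the conservative level on which the protocol was sized.
- The four-test scenario is conditional: SAP 1.2.1 names SRA for PH2.

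**Conclusion.** The concern holds. The SAP gives two incompatible rules for its primary decision and does not rank them.

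- Following the no-adjustment sentence gives a family-wise error of 9.75% under independence, against the stated 5%; positive correlation lowers it.
- The two rules disagree in 4.75% of trials if both nulls are true, 8.9% if only PH1 has an effect (ES 0.55), and about 6% to 8% if both do and 40% to 70% respond.
- PH1 power at ES 0.55 is 81% unadjusted. Under Hochberg it is 72% at the lower limit and 75% to 77% if PH2 also has ES 0.55.

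The contradiction itself rests on the text alone. The figures rest on independent tests and a t-test approximation, and those involving PH2 also on the assumed number of non-responders. The primary family below 80% agreement is a related gap that needs its own sentence.

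**What to change.** 1. State one alpha rule for PH1 and PH2. Either delete the no-adjustment sentence and keep Hochberg at family-wise 0.05, as SAP 1.1, the SAP 1.2.1 decision rule and Protocol 16.0 already say; or replace both with a pre-specified order in which each hypothesis is tested at 0.05 and the second only if the first is rejected. Align SAP 1.1, SAP 1.2.1 and Protocol 16.0 with the choice.
2. Reconcile SAP 1.2 with SAP 1.2.1 on what is primary if agreement is below 80%. Name one outcome as primary, or apply Hochberg to every primary test.
3. If Hochberg is kept, restate PH1 power at ES 0.55 as about 72% at the 0.025 threshold (the lower limit), rising towards 81% as PH2 power rises.

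The cost is SAP wording and a less favourable stated power; the fix needs no added enrolment. If 80% PH1 power at 0.025 were wanted, enrolment would be about 145 (140 by the normal approximation) against the 120 planned. A PH1-then-PH2 order keeps PH1 at 81%, but lowers PH2 from about 49% under Hochberg to about 41% at 50% responders.

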1.2 Quantitative Analysis Plan

Original Primary Hypotheses: 1. Youth randomized to CPS will have significantly greater VL suppression (primary outcome) and self-reported medication adherence (secondary outcome) at 24 weeks than those in SMS group. 2. Non-responders randomized to CPS with incentives will have significantly greater VL suppression (primary outcome) and self-reported adherence (secondary outcome) than those randomized to SMS with incentives.

Original Secondary Aims: a) Conduct an exploratory evaluation of tapering the intensity of CPS and SMS (among responders) vs termination after completion of the 24 week intervention to determine if this improves the durability of intervention effects; b) Explore the relative efficacy of the individual intervention sequences embedded within the SMART design for responders and non-responders; and c) Describe moderators of the treatment effect, including demographics, mode of infection, substance use, and mental health. [NOT COMPLETED DUE LOW RENTENTION]

Updated Primary Outcome: Originally, we plan to treat VL suppression as our primary outcome for both co-primary hypothesis. Primary end-point for H1 was at 24 weeks when the proximal outcome was used to determine responder status, while for H2 the Distal outcome was at end of 12 months (or 72 weeks). Due to the difficulty in collecting viral load we proposed to change the primary outcome to a combination of VL suppression and self-reported adherence (SRA). Primary end-points for both co-primary hypothesis is now at 48 week.

Rationale of new definition of Primary Outcome: Since the VLS data may not be available for a significant number of subjects, we plan to use SRA as an additional primary outcome. The usefulness and appropriateness of the usage of these two depends upon the concordance of two measures. To determine that for those subjects we have both VLS and SRA data available, we will first construct a 2×2 contingency table and conduct a chi-square test of association. If they agree on 80% or more cases we will proceed to define (and analyze) the primary outcome as following:

- 1) For any data collection point and randomization event, if VLS data is available it will be used as primary outcome. When VLS data is not available, SRA will be used as primary outcome. This composite definition will be used as primary outcome and will have sufficient power based on hypothesized effect size.

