
PH2. An exploratory analysis is also planned where we define a composite binary outcome as 1 if either SRA or VL suppression ($VL < 200$ copies/ML) is achieved and 0 otherwise. This binary composite outcome variable will be analyzed using mixed effect GLM. Since our modified design guarantees availability of at least one of the two defining quantities this exploratory analysis ensures usage of full data.

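### The exploratory either-or composite scores a measured viral failure as success, skips the SAP's agreement gate, and rests on an availability guarantee that the SAP contradicts

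*SAP*

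**What the plan says.** SAP 1.2.1 adds an exploratory mixed-effects GLM on a "composite binary outcome as 1 if either SRA or VL suppression" (VL below 200 copies/mL) is achieved, and 0 in every other case. Its justification begins "Since our modified design guarantees availability of at least one of the two defining quantities", and it concludes that the analysis therefore uses the full data.

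SAP 1.2 sets a different rule for the primary composite: "if VLS data is available it will be used as primary outcome. When VLS data is not available, SRA will be used as primary outcome". That rule is conditional: "If they agree on 80% or more cases we will proceed to define (and analyze) the primary outcome". Below 80% agreement, SAP 1.2 says "Two measures cannot be combined, as they do not match sufficiently" and analyses them separately.

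On missing data, SAP 1.2 mentions full SRA availability only as a proviso. SAP 1.2.4 sizes the trial "with 10% attrition assuming equal responder rate (p) in both arms". SAP 1.2.5 expects some participants not to complete and plans multiple imputation of missing outcomes for two-group comparisons.

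**The concern.** There are three problems.

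- **Direction of the rule.** Protocol 4.0 classes a VL of 200 or more at three months as non-response. The either-or rule lets a favourable self-report override that laboratory result, although SAP 1.2 brings in SRA only to fill in for a missing VL.
- **No gate.** The either-or composite has no agreement condition. It would still be run in the situation where SAP 1.2 says the measures must not be combined.
- **Stated property.** The availability guarantee is the reason given for the analysis. SRA comes from the follow-up web survey (Protocol 5.0), so someone who stops follow-up supplies neither measure. Read literally, 'otherwise' scores that visit as a failure.

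At stake is how the result would be read. Counting failures as successes raises the success rate in both arms and distorts the contrast by an amount that depends on how self-report behaves in each arm.

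**Working it through.** **1. The plan's own figure.** With two-sided alpha 0.05, 80% power and ES 0.55, n per arm = 2(1.960 + 0.842)² / 0.55² = 51.9, so 52 per arm and 104 in total. Then 52/0.9 = 57.8, so 58 per arm and 116 in total. Both match the ES 0.55, p = 0.5 row of the SAP 1.2.4 table. With 60 × 0.9 = 54 per arm, power = Φ(0.55·√27 − 1.96) = 81.5%. These figures are not in dispute.

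**2. The two rules side by side.** VL (below 200, 200 or more, missing) crossed with SRA (met, not met, missing) gives nine states. The rules agree in seven and differ in two:

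| VL | SRA | Either-or (1.2.1) | VL-first (1.2) |
|---|---|---|---|
| 200 or more | met | 1 | 0 |
| missing | missing | 0, read literally | undefined |

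The first row needs no assumption.

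**3. How large the first row can be.** At exactly 80% agreement, up to 20% of participants with both measures could be in it. For assumed suppression rates of 40%, 50%, 60% and 70%, that is 20/60 = 33%, 20/50 = 40%, 20/40 = 50% and 20/30 = 67% of all viral failures. Without a gate the share can be larger.

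**4. Equal over-reporting.** All inputs here are assumptions. True suppression is 36.4% vs 63.6%, chosen because 2·arcsin√0.636 − 2·arcsin√0.364 = 0.55. A share f = 0.34 of failures in each arm meets SRA, every suppressed participant meets SRA, and there are 54 per arm.

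- Either-or rate: q = p + (1 − p)f. This gives 0.364 + 0.636 × 0.34 = 0.580 and 0.636 + 0.364 × 0.34 = 0.760.
- VL-first rate, with VL available for a share v: v·p + (1 − v)·q. At v = 0.25 this is 0.526 vs 0.729. At v = 0.50 it is 0.472 vs 0.698.
- Power = Φ[(d − 1.96·se0)/se1], with se0 = √(2p̄(1 − p̄)/54) and se1 = √((p1(1 − p1) + p2(1 − p2))/54).
- Either-or: Φ[(0.1795 − 0.1774)/0.0888] = 51%.
- VL-first, v = 0.25: Φ[(0.2026 − 0.1824)/0.0910] = 59%.
- VL-first, v = 0.50: Φ[(0.2258 − 0.1858)/0.0923] = 67%.

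Over f from 0.20 to 0.40, either-or power runs from 64% to 46%. VL-first power runs from 69% to 55% at v = 0.25 and from 73% to 64% at v = 0.50.

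**5. Unequal over-reporting.** Assume true suppression of 50% in both arms, with 20% vs 40% of failures meeting SRA. The composite reads 0.5 + 0.5 × 0.20 = 60% vs 0.5 + 0.5 × 0.40 = 70%. The chance of a significant result favouring the higher-reporting arm is Φ[(0.10 − 0.1799)/0.0913] = 19%, against a nominal 2.5% in that direction. With 20% vs 50%, it reads 60% vs 75% and the chance is 38%. VL-first reduces this but does not remove it. For 20% vs 40% it reads 57.5% vs 65% at v = 0.25 (12%) and 55% vs 60% at v = 0.50 (8%).

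**6. Would the gate catch these cases?** Not necessarily. In step 4 the discordant share averages 0.5 × 0.34 = 17%, so agreement is 83%. In step 5 (20% vs 40%) it is 0.5 × 0.30 = 15%, so agreement is 85%. Both pass 80%, so the gate does not make the either-or rule safe.

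**7. Availability.** Planned attrition of 10% is 0.10 × 120 = 12 participants who may have neither measure at later visits. The guarantee implies none. Protocol 13.0 also provides for withdrawal after baseline with removal from follow-up contact, and SAP 1.2 records low retention.

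**The case against.** The strongest defence is the label: "An exploratory analysis is also planned where we define a composite binary outcome". An exploratory outcome may differ from the primary one, and no primary hypothesis depends on this one. The VL-first rule is itself not settled, since SAP 1.2.1 names SRA alone as primary and says VL suppression no longer is. This stands, and it limits the weight of the point. It does not explain why a measured failure should count as success, or why the agreement condition is dropped.

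Second, SAP 1.2.5 lets mixed models use whatever data exist, so 'otherwise' can be read as measured and not achieved. That is a fair reading, and a reader should not conclude that dropouts will certainly be coded as failures. The text allows both readings and should state one.

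Three stronger inferences are tempting and not supported:

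- **Power falls from about 81% to 51%.** The 81% requires a measured VL for all 54 per arm. SAP 1.2 expects VL to be missing for many, and a VL-first composite also uses SRA for those. The fair comparison is 51% against 59-67%.
- **The protocol supplies the 34%.** The 34% in Protocol 2.0 concerns youth with detectable VL who had reported an undetectable result at their last medical visit. That is recalled VL at an earlier date, not adherence. It serves here only as an illustrative value.
- **The rule always shrinks the difference.** That holds under equal over-reporting. Step 5 shows that unequal over-reporting can create a difference.

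**Conclusion.** The rule and its justification are wrong as written, in an exploratory analysis. That a measured VL of 200 or more with SRA met counts as success, that the 80% gate is absent, and that the availability claim conflicts with SAP 1.2, 1.2.4 and 1.2.5 all follow from the text without assumptions.

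The size of the effect does rest on assumptions. Under equal over-reporting of 34%, the either-or rule costs about 8 to 16 points of power relative to a VL-first rule with VL available for 25-50%. Under the unequal example it gives about a 19% chance of a significant result with no viral difference. These figures use a single-visit two-proportion test, whereas the planned model is longitudinal and carries no power claim of its own. They show direction and rough scale only. A reader might infer that the primary conclusions are compromised. The documents do not support that.

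**What to change.** In SAP 1.2.1:

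- Define the composite as VL suppression when VL is available and SRA only when it is not, subject to the 80% agreement condition in SAP 1.2.
- If the either-or version is kept, label it a sensitivity analysis and report by arm the number of participants with VL of 200 or more and SRA met.
- State that visits with neither measure are missing and are handled under SAP 1.2.5, not scored 0.
- Delete the sentence on guaranteed availability and full data.
- State what counts as SRA achieved. The only SRA threshold in the documents is the eligibility criterion in Protocol 9.0.

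The VL-first version will largely coincide with the SAP 1.2 composite, so the sponsor may prefer to keep this analysis only as the labelled sensitivity analysis. The cost is SAP wording, with no new data or procedures.
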